5. STUDY POPULATION

5.1. General

The ITT analysis set (Section 3.1) will be used for all study population summaries, unless otherwise specified. The summaries might be presented using the mITT analysis set (Section 3.2), in case >10% of ITT patients were excluded from the mITT analysis set. Summaries will be presented by treatment group and for all patients.

5.2. Patient Disposition

Data from patients screened; patients screened but not randomized (and reason not randomized); patients who are randomized; patients randomized but not treated; patients re-randomized (if applicable); patients in the ITT, mITT, safety, PP, MITTA and MITTB analysis sets; patients who complete the treatment period; patients who withdraw from the study during the treatment period; patients who complete the EOS visit; and patients who withdraw from the study will be summarized using descriptive statistics.

Data from patients who withdraw from the study during the treatment period, and from the study overall will be summarized by reason for withdrawal.

Data from patients who withdraw during the treatment period will be summarized by classification to MAR/MNAR overall, for the titration and maintenance periods, and by visit using descriptive statistics.

5.3. Demographics and Baseline Characteristics

Patient demographic and baseline characteristics will be summarized using descriptive statistics.

The continuous variables of patient age, weight, height, and body mass index (BMI) will be summarized using descriptive statistics.

BMI at baseline will be computed as:

$$\text{BMI (kg/m}^2\text{)} = \text{Weight at baseline (kg)} / [\text{Height at screening (m)}^2].$$

Height, weight, and BMI at baseline will also be presented by age group and sex using descriptive statistics. In addition, normal age and sex-based z-scores and percentiles for BMI will be determined using the World Health Organization (WHO) growth charts, and summarized descriptively.

The categorical variables of patient weight group, sex, race, ethnicity, and region (United States (US) and non-US) and country for non-US will be summarized using descriptive statistics for each category. The categorical variables of age group at baseline (6 to <12 years, 12 through 18 years, inclusive), use of a strong CYP2D6 inhibitor, as appears in Table 9 of the study protocol (Yes/No), CYP2D6 genotype (Poor CYP2D6 metabolizer/ Non-poor CYP2D6 metabolizer), and CYP2D6 impairment status (Impaired/Not impaired) will be summarized using descriptive statistics for each category. In addition, age and sex-based BMI categories include: Underweight (< 5 percentile), Normal (≥ 5 - < 85 percentile), Overweight (≥ 85 - < 95 percentile), Obese (≥ 95 percentile), will be tabulated for each category.

5.4. Disease Characteristics

Post-hoc analysis will be provided for disease characteristics.

5.5. Medical History

All medical history will be coded using the Medical Dictionary for Regulatory Activities (MedDRA). The incidence of medical history abnormalities will be summarized using descriptive statistics by system organ class (SOC) and preferred term. Patients are counted only once in each preferred term and SOC category. Summaries will be presented by treatment group and for all patients.

5.6. Prior Therapy and Medication

Any prior or concomitant medication a patient has had within 3 months prior to baseline and up to the end of study, including follow up, will be recorded on the CRF. Generic or trade name, indication, dose, and start and end dates of the administered medication will be recorded. The sponsor will encode all medication according to the WHO drug dictionary.

The incidence of prior therapies and medications will be summarized using descriptive statistics by therapeutic class, preferred base name and preferred term. Patients are counted only once in each therapeutic class category, and only once in each preferred term category. Prior therapies and medications will include all medications taken and therapies administered before the first day of IMP administration.

5.7. Study Drug Titration

The number and percent of patients at each dose level by weight group and CYP2D6 impairment status during the titration period will be summarized by week. The latest administered dose in each study week will be used.

Reasons for the deviation from the IMP dosing scheme (see Protocol Sections 5.1.1.1 and 5.1.1.2) will be summarized overall and by period (titration and maintenance). Patient data will be reviewed in the blinded SDR meeting prior to database lock to determine the reason for deviation in each period and overall.

Descriptive statistics of the maintenance dose (last dose taken in the maintenance period); nominal and as percent of the maximal planned dose for the patient) will be presented.

The safety analysis set will be used for IMP titration summaries.

5.8. Study Drug Compliance

Study drug compliance during the treatment period will be assessed as described in the protocol Section 5.7.

Study drug compliance will be determined by presenting the number of tablets taken as a percentage of the expected number of tablets based on the dose(s) of the patient at the relevant time period (see [Table 4](#) and [Table 5](#); study protocol Section 5.1).

Table 4: Drug Kits based on Titration Scheme – Non-Impaired CYP2D6 Metabolizers

Weight Group	12kg to <17kg		17kg to <30kg		30kg to <40kg		≥40kg	
	Dose (mg/day)	Tablets (mg)	Dose (mg/day)	Tablets (mg)	Dose (mg/day)	Tablets (mg)	Dose (mg/day)	Tablets (mg)
Day 2	6	6	6	6	6	6	6	6
Week 1	6	6	6	6	6	6	12	6,6
Week 2	6	6	12	6,6	12	6,6	18	9,9
Week 3	12	6,6	18	9,9	18	9,9	24	12,12
Week 4	12	6,6	18	9,9	24	12,12	30	15,15
Week 5	18	9,9	24	12,12	30	15,15	36	18,18
Week 6	18	9,9	24	12,12	36	18,18	42	15,6 AM 15,6 PM
Week 7	24	12,12	30	15,15	42	15,6 AM 15,6 PM	48	12,12 AM 12,12 PM

Dose and tablets refer to IMP, either TEV-50717 or matching placebo. Maximal dose according to the titration scheme is presented.

Table 5: Drug Kits based on Titration Scheme –Impaired CYP2D6 Metabolizers

Weight Group	12kg to <17kg		17kg to <30kg		30kg to <40kg		≥40kg	
	Dose (mg/day)	Tablets (mg)	Dose (mg/day)	Tablets (mg)	Dose (mg/day)	Tablets (mg)	Dose (mg/day)	Tablets (mg)
Day 2	6	6	6	6	6	6	6	6
Week 1	6	6	6	6	6	6	12	6,6
Week 2	6	6	12	6,6	12	6,6	18	9,9
Week 3	12	6,6	18	9,9	18	9,9	24	12,12
Week 4	12	6,6	18	9,9	24	12,12	30	15,15
Week 5	12	6,6	18	9,9	24	12,12	36	18,18
Week 6	12	6,6	18	9,9	24	12,12	36	9,9 AM 9,9 PM
Week 7	12	6,6	18	9,9	24	6,6 AM 6,6 PM	36	9,9 AM 9,9 PM

Dose and tablets refer to IMP, either TEV-50717 or matching placebo. Maximal dose according to the titration scheme is presented.

The number of tablets used is the number of tablets dispensed minus the number of tablets returned. If a patient does not return a pill bottle, it will be assumed that the patient took no IMP from that bottle for the purposes of calculating compliance.

The denominator of “expected number of tablets” will be calculated based on patients’ participation in the study (ie, last day of study drug – first day of study drug + 1) and the

expected dose according to the RTSM system. Adjustments may be required for the doses split between the morning and the evening dose. Of note, the protocol allows the investigator not to titrate a patient up to the maximal possible dose by weight group and CYP2D6 impairment status; therefore the expected number of tablets will be calculated individually. Moreover, drug suspensions and reductions based on investigator instructions are considered as change in the expected number of tablets and are not considered non-compliance. For patients who complete the study, the last day of study drug used in the denominator calculation will be the last expected dosing day. For early termination patients, the last day of study drug used in the denominator calculation will be the last expected dosing day before termination day.

A patient will be deemed compliant over the treatment period if the patient has taken 80% to 105% of the expected tablets of study drug.

Treatment compliance (%) will be summarized as continuous data using descriptive statistics. In addition, treatment compliance will be summarized as categorical data using descriptive statistics for the following categories: <80%, 80% to 105%, >105%. Compliance will be presented by visit, by overall in the titration and maintenance periods, and by overall in the treatment period.

An additional assessment of the IMP compliance may be performed while taking into account the patient's dose.

5.9. Study Protocol Deviations

Data from patients with any important protocol deviations (as recorded in the Clinical Trial Management System) during the study will be summarized overall and for each category using descriptive statistics. All protocol deviations will be listed.

In addition, patients with any COVID-19 related protocol deviations will be summarized and listed separately.

Reasons for exclusion from the PP analysis set (as evaluated in the final blinded statistical data review meeting; see Section 3.4) will be summarized using descriptive statistics.

6. EFFICACY ANALYSIS

6.1. General

The mITT, mITTA, mITTB, ITT, and PP analysis sets (Section 3) will be used for all the efficacy analyses.

The mITT analysis set will be regarded as the main set for the analysis of the primary endpoint. It will also be used for all the efficacy endpoints unless otherwise specified. In addition, the mITTA, mITTB, ITT, and PP analysis sets will be used for the sensitivity analyses of the primary and key secondary endpoints.

Summaries will be presented by each scheduled visit (until Week 15) and treatment group, unless specified otherwise.

All p-values for treatment effect (TEV-50717 vs. placebo) will correspond to a 1-sided test for superiority.

6.2. Primary Efficacy Endpoint and Analysis

6.2.1. Primary Endpoint

6.2.2. Definition

The primary efficacy endpoint is the change from baseline to week 15 in the MD-CRS part II total score (movement disorder severity, centrally read) (TEV-50717 versus placebo).

6.2.3. Primary Efficacy Analysis

The primary analysis will be a mixed-model repeated-measures (MMRM) with the change in MD-CRS part II total score as the dependent variable. The model will include fixed effects for treatment group, week (as a categorical variable with 3 levels: weeks 9, 12, and 15), and treatment group by week interaction. The baseline MD-CRS part II total score, age group at baseline (2 levels: 6 to <12 years; 12 through 18 years, inclusive), and region (US; non-US) will be included as covariates. The unstructured covariance matrix will be used in the model. In cases where the model does not converge, the Maximum-Likelihood estimation method will be used instead of the default Restricted Maximum-Likelihood. If the model still does not converge, then a simpler covariance structure with fewer parameters will be used, according to the following order: Heterogeneous Autoregressive (1), Heterogeneous Compound Symmetry, Autoregressive (1), and Compound Symmetry. The Kenward-Roger approximation will be used to estimate denominator degrees of freedom.

Missing data will be classified as MAR and MNAR, as described in Section 4.3. MNAR data will be imputed using the jump-to-reference method, and MAR data will be imputed based on the randomized treatment group. The details are described below:

1. Missing data will be imputed in 2 separate subgroups. The MAR subgroup will contain all patients randomized to a TEV-50717 treatment group without missing data at week 15 or have a MAR missing data mechanism. The MNAR subgroup will contain all patients randomized to placebo as well as patients randomized to receive TEV-50717 with missing data at week 15 with an MNAR missing data mechanism.
2. Data will be imputed for patients with missing data at week 15 using a predictive mean matching multiple imputation method. Multiple imputations will be performed within each subgroup:
 - a. Under a MNAR data assumption, patients in the MNAR subgroup will have their missing data at week 15 imputed as if they behaved like placebo treated patients after dropping out. Only placebo patients with complete data will be included in the imputation model.
 - b. All other patients will have data imputed from a model derived from their assigned treatment group (imputation under MAR assumption).

The imputation models will include age group at baseline, region, baseline MD-CRS part II total score, and MD-CRS part II total scores at week 9 and week 12. After obtaining complete data sets for both subgroups, they will be combined and the complete data set will be used in the analysis.

3. The resulting complete, imputed datasets will each be analyzed using the analysis model described above and the resulting statistics combined using methodology presented by [Rubin \(1987\)](#) and [Little and Rubin \(2002\)](#).

The complete multiple imputation methodology, along with SAS code, is detailed in [Appendix 1](#). Difference in least squares (LS) mean of the change in MD-CRS part II total score from baseline to week 15 (TEV-50717 versus placebo) will be compared using a 1-sided test for superiority at a nominal significance level of $\alpha=0.025$.

The LS mean and SE for the treatment groups, the LS mean difference, 2-sided 95% confidence interval, and p-value for the comparison (TEV-50717 versus placebo) at week 15 will be presented.

6.2.4. Sensitivity Analysis

To assess the robustness of the primary efficacy analysis, sensitivity analyses will include the following:

Sensitivity analyses for assumptions of missing data mechanism:

- tipping point (MNAR)
- MAR multiple imputation

Sensitivity analysis for the statistical model:

- analysis of covariance (ANCOVA)
- primary model, including only the following covariates: treatment group, week, and treatment group by week interaction

Other:

- primary model repeated for the ITT analysis set;
- primary model repeated for the mITTA analysis set;
- primary model repeated for the mITTB analysis set;
- primary model repeated for the PP analysis set;
- ANCOVA models for MD-CRS part II total score change from baseline to week 9 and to week 12.

6.2.4.1. Sensitivity Analyses for Assumptions of Missing Data Mechanism

Sensitivity analyses for assumptions of missing data mechanism include the MNAR tipping point analysis and the MAR multiple imputations.

6.2.4.1.1. MNAR Tipping Point Analysis

Details for tipping point analysis are described below:

- a. For patients that completed the study, intermittent missing data are considered as MAR and will be imputed by the predictive mean matching multiple imputation method (Heitjan and Little 1991, Schenker and Taylor 1996). The imputation model will include age group at baseline, region, treatment group and MD-CRS part II total score at baseline, week 9 and week 12.
- b. For patients who discontinued due to any reason, all missing data will be imputed using the same predictive mean matching multiple imputation method. The imputed values will be adjusted under a MNAR assumption:
 - Patients randomized to TEV-50717: the first missing value after patients drop out will be analyzed assuming the treatment effect is worsened by δ (where $\delta_1 = 0$ to 2 or estimated treatment effect based on the primary analysis, whichever is higher, in step of 0.2) compared to the patients who have no missing value. $\delta \geq 0$ will be used as a shift to adjust the imputed values, since higher MD-CRS score corresponds to the more severe movement disorder.
 - Patients treated with placebo: the observed treatment effect for placebo-treated patients will be used for imputing missing value in the placebo population for all shift parameters.

The shift will be applied only for the first visit with missing data and will not be applied for later time points as these values are shifted through the condition on the previous time points. For each δ value, 500 imputed datasets will be obtained.

- c. The resulting complete, imputed datasets will each be analyzed using the same model as the primary analysis model, and the resulting statistics combined using methodology provided by Rubin (1987) and Little and Rubin (2002). Refer to Appendix 1; start at Step 2.

The complete multiple imputation methodology, along with the SAS code, is detailed in Appendix 2.

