APPENDIX 2. TIPPING POINT ANALYSIS

Let delta (shift) be the penalty to TEV-50717 group, ie. the worsening of effect for the patients in TEV-50717 group who early dropped out, compared to patients with full data, assuming MNAR. Delta will be in the range of 0 to 2 (or estimated treatment effect from primary analysis if it is larger than 2) in step of 0.2. The following 3 steps will be performed to do the multiple imputation analysis:

1. Create complete data sets using imputation for each shift in treatment effect.
2. Analyze the imputed complete data sets for each shift in treatment effect.
3. Combine analysis results into a final result for each shift in treatment effect.

Step 1:

The fully conditional specification (FCS) method will be used to impute missing values for MD-CRS part II total score change values and will use age group at baseline, treatment arm, and baseline MD-CRS part II total score to determine the scores (500 imputations will be created).

The SAS code for the imputation is as follows:

```
%macro midata(data=, smin=, smax=, sinc=, out=);  
data &out; set _null_; run;  
%let ncase=%sysevalf((&smax-&smin)/&sinc, ceil);  
%do jc=0 %to &ncase;  
%let sj=%sysevalf(&smin + &jc*&sinc);  
proc mi data=&data out=outmi seed=724375 nimpute=500;  
class arm agegrp region;  
fcs regpmm;  
mnar adjust (_9 /shift=&sj adjustobs=( arm='TEV-50717'));  
mnar adjust (_12 /shift=&sj adjustobs=( arm='TEV-50717'));  
mnar adjust (_15 /shift=&sj adjustobs=( arm='TEV-50717'));  
  
var arm agegrp region base _9 _12 _15; run;  
data outmi; set outmi; shift=&sj; run;  
data &out; set &out outmi; run;  
  
%end;  
%mend midata;  
  
%midata(data=final, smin=, smax=, sinc=, out=out1);
```

Values should be added for smin, smax, and sinc. Per current definitions, these should be smin=0, smax=2.0 (or estimated treatment effect from primary analysis if it is larger than 2) and sinc=0.2.

Step 2

The resultant complete data sets will be analyzed using the same model as the primary analysis – see [Appendix 1](#) - Step 2. The SAS code is as follows:

```
data all; set out1;
  avisitn=9; chg=_9; output; avisitn=8; chg=_8; output; avisitn=12; chg=_12; output; run;

proc sort data=all; by shift _imputation_ arm avisitn; run;

proc mixed data=all order=data; by shift _imputation_ ;
  class usubjid arm avisitn agegrp region;
model chg=arm avisitn arm*avisitn agegrp region base / ddfm=kr;
  repeated avisitn / type=un subject=usubjid;
  lsmeans arm*avisitn / diff cl;

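### The tipping-point shift is specified in two conflicting ways, and under neither is delta the week-15 penalty for TEV-50717 dropouts first missing before week 15

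*SAP*

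**What the plan says.** Section 6.2.4.1.1 separates two kinds of missing data. Intermittent gaps in patients who completed the study are treated as MAR and are not shifted. For TEV-50717 patients who discontinued, "the first missing value after patients drop out will be analyzed assuming the treatment effect is worsened by" delta. The section then says "The shift will be applied only for the first visit with missing data and will not be applied for later time points", giving as its reason "as these values are shifted through the condition on the previous time points".

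The grid for delta runs from 0 to 2 in steps of 0.2. Appendix 2 extends the upper limit with the words "or estimated treatment effect from primary analysis if it is larger than 2". The primary estimate is the week-15 difference in LS means (Section 6.2.3).

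Section 6.2.4.1.1 closes with "The complete multiple imputation methodology, along with the SAS code, is detailed in Appendix 2". Step 1 of Appendix 2 uses FCS with predictive mean matching. It carries one adjustment line per visit, starting "mnar adjust (_9 /shift=&sj adjustobs=( arm='TEV-50717" and "mnar adjust (_12 /shift=&sj adjustobs=( arm='TEV-50717", with a matching line for _15. The only condition in each line is the treatment arm. Nothing limits the shift to the first missing visit or to patients who discontinued.

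**The concern.** A tipping point is useful only if the reader knows what delta means at the endpoint visit. Here the endpoint is week 15 and the grid limit is a week-15 quantity, so a statement that the result holds up to a delta of 2 will be read as a loss of 2 points at week 15.

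Under the text, a shift added at week 9 or 12 reaches week 15 only after multiplication by regression slopes. Patients first missing at week 15 take the full delta, earlier dropouts take some other amount, and no rationale is given for that dependence on timing. Under the code, the shift is added again at each later visit on top of what conditioning already carries, and completers' intermittent gaps are penalised too. Whoever programs the analysis must choose between two rules that can move the reported tipping point in opposite directions.

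**Working it through.** **Inputs from the SAP (Section 2.4).** SD 3.5; about 43 TEV-50717 and 22 placebo patients; expected MNAR rate 10%; difference 2.0 diluted to 1.8; 1-sided alpha 0.025.

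**The plan's own figures.** 2.0 × (1 − 0.10) = 1.8, as stated. For a difference of 1.8, SD 3.5, 2:1 allocation and 90% power, the normal formula gives 180 patients against the stated 185. Power at 124/61 is 0.908. These inputs are consistent. The SAP gives no figure for how much of delta reaches week 15.

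**Assumptions.** The SAP gives no correlation between visits. I take ρ from 0.5 to 0.9, compound symmetry (CS) or AR(1), equal variances at weeks 9, 12 and 15, baseline omitted, and imputation in visit order.

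**Slopes.** Let b9 and b12 be the slopes of week 15 on weeks 9 and 12.
- CS: b9 = b12 = ρ/(1+ρ).
- AR(1): b9 = 0 and b12 = ρ.
- The slope of week 12 on week 9 is ρ in both.

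**Text rule (shift once, at the first missing visit).**
- First missing at week 12: b12. CS gives 0.5/1.5 = 0.33 to 0.9/1.9 = 0.47; AR(1) gives 0.50 to 0.90.
- First missing at week 9: b9 + b12·ρ. CS gives ρ, 0.50 to 0.90; AR(1) gives ρ², 0.25 to 0.81.
- First missing at week 15: 1.00.

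**Appendix 2 code (shift at every imputed visit).**
- First missing at week 12: 1 + b12. CS 1.33 to 1.47; AR(1) 1.50 to 1.90.
- First missing at week 9: 1 + b9 + b12(1+ρ). CS 1.83 to 2.37; AR(1) 1 + ρ + ρ², 1.75 to 2.71.

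**At ρ = 0.7, as multiples of delta at week 15:**

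| First missing | Text, CS | Text, AR(1) | Code, CS | Code, AR(1) |
|---|---|---|---|---|
| Week 12 | 0.41 | 0.70 | 1.41 | 1.70 |
| Week 9 | 0.70 | 0.49 | 2.11 | 2.19 |

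A simulation with predictive mean matching (43/22, SD 3.5, delta 2, ρ = 0.7) gave 0.39 and 0.67 for the text rule at week 12, and 0.62 and 0.38 at week 9. For the code it gave 1.37 and 1.66, then 2.03 and 2.03. Under the text rule, a reported delta of 2 therefore means roughly 2 × 0.41 = 0.8 to 2 × 0.70 = 1.4 at week 15.

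**Effect on the estimate.** Erosion of the week-15 difference = dropout share × delta × multiple. The standard error is 3.5 × √(1/22 + 1/43) = 0.92. With 10% TEV-50717 dropouts, delta 2 and ρ = 0.7:
- Exactly delta at week 15: 0.10 × 2 × 1.00 = 0.20 (0.22 SE).
- Text rule: 0.10 × 2 × 0.41 to 0.70 = 0.08 to 0.14 (0.09 to 0.15 SE).
- Code, first missing at week 12: 0.10 × 2 × 1.41 to 1.70 = 0.28 to 0.34 (0.31 to 0.37 SE).

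With 20% dropouts (an assumption), the first two become 0.44 SE and 0.18 to 0.31 SE.

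**Who is affected.** The mITT set requires a post-baseline central reading (Section 3.2). Table 2 files an early-termination MD-CRS from day 2 to 73 as week 9. First missing at week 12 should then be the main early pattern and first missing at week 9 uncommon. The exception is a reading dated after end of treatment, which Table 2 sends to week 16.

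**The case against.** A reader might infer from the text rule alone that the planned analysis overstates robustness. The documents do not support that as a general conclusion, for four reasons.

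- **The code points the other way.** Section 6.2.4.1.1 defers to Appendix 2 for the complete method, and the printed program over-penalises earlier dropouts.
- **Delta is openly defined at the first missing value.** A first-visit shift carried forward is a coherent MNAR model, so patients do not receive less than the text promises. This stands. However, Appendix 2 describes delta more broadly as the worsening for early dropouts relative to patients with full data, both places scale the grid to the week-15 effect, and the SAP does not plan to report the implied week-15 shift.
- **Attenuation is not guaranteed.** Appendix 2 specifies FCS. If shifted values feed back into the chain (an assumption), the text rule at ρ = 0.7 gives 0.50 (CS) or 1.04 (AR(1)) of delta for first missing at week 12, and 1.65 or 0.96 for week 9. Slopes also scale with the ratio of visit SDs: under AR(1) with ρ = 0.9, the week-12 slope exceeds 1 once SD15/SD12 passes 1/0.9 = 1.11. This stands, and it makes delta harder to interpret under the text rule.
- **The stakes are limited.** This is a sensitivity analysis outside multiplicity control (Section 7), and the primary analysis already imputes MNAR data by jump to reference. This stands too.

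Omitting baseline does not inflate the text-rule attenuation. If baseline shares the same CS correlation, the share for first missing at week 12 falls to ρ/(1+2ρ), or 0.25 to 0.32, and for week 9 to ρ/(1+ρ), or 0.33 to 0.47.

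**Conclusion.** The point holds as an inconsistency in specification. Text and code apply different shifts to different patients, and neither makes delta the week-15 penalty for TEV-50717 patients first missing at week 9 or 12. Read visit by visit, the text delivers 0.33 to 0.90 of delta (first missing at week 12) or 0.25 to 0.90 (week 9), and the code 1.33 to 2.71 times delta. These ranges rest on assumed correlations and equal visit variances. The direction of any bias in the reported tipping point depends on which version is run.

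The size is modest: at 10% dropout, delta 2 and ρ = 0.7, the text rule falls 0.06 to 0.12 points short of an exact week-15 shift, against a standard error of 0.92. The MAR analysis at delta = 0 (Section 6.2.4.1.2) is unaffected, because the two rules coincide there. The conflict should be resolved before database lock; it does not threaten the primary test.

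**What to change.** State one rule in both places. Preferred:

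1. In Section 6.2.4.1.1 b, impute all missing visits under MAR. Then add delta once, after imputation, to each imputed post-discontinuation value of TEV-50717 discontinuers. Week 15 then carries exactly delta, whatever the first missing visit, the correlation or the imputation algorithm.
2. Delete the sentence that relies on carry-through.
3. In Appendix 2 Step 1, replace the MNAR ADJUST lines with a data step after PROC MI that selects discontinuers and leaves completers' intermittent gaps unshifted.
4. Apply the same rule to the key secondary tipping-point analyses (Section 6.3.1.2).

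If the first-visit rule is kept, make the code follow it, restrict it to discontinuers, and report the implied mean week-15 shift beside each delta.

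While the code is open, correct the visit output in Appendix 2 Step 2. It lists weeks 9, 8 and 12 and so produces no week-15 result.

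The cost is an SAP wording change and a short data step, and the reported tipping delta will change. Section 2.5.1 bars changes to the main analyses after the interim; this is a sensitivity analysis, so that restriction does not stand in the way.
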